The scores will be derived in accordance with the FACT-O Scoring Manual. A number of items are negatively stated and need to be reversed by subtracting the response from "4". The scoring manual identifies that the following items need to be reversed prior to summarising: GP1-7, GE1, GE3-6, O1-3, C2, and B5. After reversing proper items, scores are summarised and multiplied by the number of items in the domain. For each subscale (domain), if less than 50% of the subscale items are missing, the subscale score will be divided by the number of non-missing items and multiplied by the total number of items on the subscale. If at least 50%

of the items are missing, that subscale also will be treated as missing. The reason for any missing assessment will be identified. If data are missing at random, the above techniques will be used. If there is evidence that the missing data are systematic, missing values will be handled to ensure that any possible bias is minimised. The TOI score ranges from 0-100 and the FACT-O from 0-152. For all Functional Assessment of Chronic Illness Therapy (FACIT) scales and symptom indices, a higher score indicates a higher HRQoL.

The actual change from baseline in TOI score will be derived for each visit where there is available data. For example; at visit X, the calculation will be (TOI score at visit X – baseline TOI score). Actual change from baseline for the individual FACT-O subscale scores will be calculated in a similar way. The baseline score is defined as last non-missing score prior to dosing with study treatment (olaparib or placebo). Any questionnaires completed on day 1 of dosing will be considered pre-dose.

A change of at least 10 points in TOI will be considered as a clinically relevant or a minimally important difference (Osobo et al 2005).

The threshold for a clinically important change is outlined below (Table 5):

Table 5 Health-Related Quality of Life

Score	Change from baseline	Visit response
TOI	≥+10	Improved
	≤-10 or "Subject too heavily affected by symptoms of disease under investigation" is answered as the reason for not completing HRQoL at visit.	Worsened
	Otherwise	No change

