During the randomised treatment phase, it is expected that olaparib will not cause harm to HRQoL, this will be demonstrated by comparing the Trial Outcome Index (TOI) best response rates (improved/no change/worsened) whilst on randomised treatment. A contingency table summarising the TOI best change rates will be provided and a CMH analysis including the randomisation stratification factor will be performed.

Date 15 February 2022

An AUC (Area Under the Curve) analysis will also be performed for TOI. For each patient, the AUC will be derived using the trapezoidal rule and including all available scheduled visits. Time-adjusted AUC will be calculated as AUC divided by time from baseline to last HRQoL visit where the patient provides data. The mean time-adjusted AUC will be analysed using analysis of variance (ANOVA) including using the same stratification factor as described for the primary analysis of PFS. Time-adjusted AUC summary statistics (mean, median, minimum, maximum, StD) per treatment arm will be presented. In addition, the analysis table will provide the estimated mean difference between treatment groups, 95% CI and p-value. This analysis will done using the first 24 months of data provided by a patient. For this analysis, for any patient who dies during the first 24 months, data for each question in the FACT-O from the time of death until 24 months will be set to 0. In addition, an analysis using all available data for each patient will be performed.

If deemed appropriate alternative methods may be used (e.g. piecewise linear modelling).

Descriptive statistics and graphs will be reported for the TOI by visits as well as change in these scores from baseline.

Total FACT-O and subscales scores

Descriptive statistics, by visit and change from baseline, will be reported for physical well-being (PWB), functional well-being (FWB) and the ovarian cancer subscale (Additional Concerns) domains. Descriptive statistics will also be provided for the individual questions that make up the additional concerns subscale.

Descriptive statistics, by visit and change from baseline, will also be reported for the emotional well being (EWB) and social well being (SWB) subscales, these two subscales do not form part of the TOI itself.

FACT-O questionnaire compliance (overall compliance and by visit compliance) will be summarised for each treatment group.

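### The TOI AUC analysis scores a dead patient 48 out of 100 and leaves the time after death out of the divisor, so dying raises time-adjusted quality of life

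*SAP*

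**What the plan says.** SAP 4.2.9 states that "An AUC (Area Under the Curve) analysis will also be performed for TOI", alongside the primary MMRM of change from baseline. For each patient "the AUC will be derived using the trapezoidal rule and including all available scheduled visits". The standardisation follows: "Time-adjusted AUC will be calculated as AUC divided by time from baseline to last HRQoL visit where the patient provides data". On the test, "The mean time-adjusted AUC will be analysed using analysis of variance (ANOVA) including using the same stratification factor" as for PFS; baseline TOI is not mentioned. The results table gives a treatment difference, 95% CI and p-value. The window is set by "This analysis will done using the first 24 months of data provided by a patient", and for a patient who dies inside it "data for each question in the FACT-O from the time of death until 24 months will be set to 0".

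Scoring is in SAP 3.3.1. The TOI sums physical well-being (7 items), functional well-being (7) and the ovarian subscale (11), has a range of 0-100, and higher is better. Negatively worded items are scored as 4 minus the response: "The scoring manual identifies that the following items need to be reversed prior to summarising: GP1-7, GE1, GE3-6, O1-3, C2, and B5".

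The SAP does not say that the zeros apply after reversal, that the TOI itself becomes 0, or that the divisor extends to 24 months for patients who die. The protocol's PRO analysis section (12.2.3.6) has no AUC analysis.

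**The concern.** The evident purpose of the death rule is to make death count as the worst outcome, so that a patient who dies is not represented only by her better, earlier scores. Two features of the wording defeat that.

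1. The zero is put on the questions, and reversal comes later as a scoring step. A response of 0 to a negatively worded item is the best answer to it, so a dead patient receives full marks for physical well-being.
2. The area is extended past death but the divisor is not. The result is no longer an average over the period it covers.

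A rule that raises the score of patients who die, most of all those who die early, biases the comparison towards the arm with more deaths in 24 months. Values above 100 would also inflate the standard deviation and appear as the reported maximum.

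A smaller point is that the ANOVA leaves out baseline TOI, although the MMRM of the same instrument adjusts for it and for its interaction with visit.

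**Working it through.** **Inputs from the SAP.** Item counts, reversal rule, reversed items and 0-100 range: 3.3.1. AUC rule, divisor and death rule: 4.2.9. Scheduled visits in the window (also 4.2.9): baseline and weeks 4, 12, 24, 36, 48, 60, 72, 84, 96.

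**Assumptions, not in the documents.** Constant TOI before death, the timing of the last visit and of death, and 24 months taken as 104 weeks.

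**Reproducing the stated range.** 25 items × 4 = 100, which matches.

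**TOI when every response is 0.**
- Physical: GP1-7 reversed, 7 × (4 − 0) = 28
- Functional: none reversed, 0
- Ovarian subscale: O1-3, C2 and B5 reversed, 5 × 4 = 20
- TOI = 28 + 0 + 20 = 48

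The reversed GE items belong to emotional well-being, which is outside the TOI. The SAP does not map O1-3, C2 and B5 to a subscale; they are placed in the ovarian subscale by elimination. Without them the score would still be 28.

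**Time-adjusted AUC.** Let a be the constant TOI before death, L the week of the last visit with data, D the week of death, d the TOI imputed after death, and E the end of the window:

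AUC = a·L + ½(a + d)(D − L) + d(E − D)

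As written, this is divided by L, giving a + [½(a + d)(D − L) + d(E − D)]/L. The bracket is positive whenever a > 0, D > L and d ≥ 0. The result therefore exceeds the patient's own pre-death mean even at d = 0.

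*Example 1: a = 75, L = 36, D = 40, E = 104.*
- As written (d = 48): 2700 + 246 + 3072 = 6018; 6018/36 = 167.2
- d = 0, written divisor: 2700 + 150 = 2850; 2850/36 = 79.2
- d = 0, divisor 104: 2850/104 = 27.4

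*Example 2: a = 75, L = 12, D = 20, E = 104.*
- As written: 900 + 492 + 4032 = 5424; 5424/12 = 452
- d = 0, written divisor: 1200/12 = 100
- d = 0, divisor 104: 1200/104 = 11.5

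**Scheduled visits only, window ending at week 96.** The first imputed value then falls at the next scheduled visit. Example 1 becomes (2700 + 738 + 2304)/36 = 159.5 as written, and (2700 + 450)/36 = 87.5 with d = 0. The direction is unchanged.

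For a patient at 70 with last visit at week 48, the four combinations on this grid are:

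| TOI after death | Divisor | Result (pre-death mean 70) |
|---|---|---|
| 48 | 48 weeks (as written) | 5796/48 = 120.8 |
| 0 | 48 weeks | 3780/48 = 78.8 |
| 48 | 96 weeks | 5796/96 = 60.4 |
| 0 | 96 weeks | 3780/96 = 39.4 |

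As written, the same patient scores 219.5 with a last visit at week 24 and 87.8 at week 72, so the rise is larger the earlier the last visit before death. It appeared in every case tested (TOI 40 to 90; last visit at week 24, 48 or 72).

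**Effect on the comparison.** The documents give no number of deaths in 24 months. In the week-48 case each death is mis-scored by 120.8 − 39.4 = 81.4 points. If the arms differed by an assumed 2 to 5 percentage points in deaths, the mean difference would shift by 0.02 × 81.4 = 1.6 to 0.05 × 81.4 = 4.1 points. The SAP's clinically relevant change is 10 points.

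**Baseline covariate.** Adjusting for baseline multiplies residual variance by about 1 − r². For an assumed r of 0.5 to 0.7 that is a reduction of 25% to 49%.

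**The case against.** The strongest reply is that the SAP is loosely worded rather than wrong. Since higher is better, a zero at death plausibly means the worst score. Imputed records might also count as data, which would carry the divisor to the end of the window. With both readings together, the patient at 70 falls to 39.4, as intended.

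Both changes are needed, and the SAP states neither. With scored zeros alone, the divisor still prevents death from lowering the result (78.8). With the longer divisor alone, death scores 48, and a patient below 48 improves by dying: at a constant 40 with last visit at week 48, (1920 + 528 + 1728)/96 = 43.5. A dead patient does not provide data in the ordinary sense of those words.

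Several points on the other side do stand:
- The examples are hypothetical patients, and the between-arm effect depends on death counts that the documents do not give.
- The AUC is an additional analysis. The primary FACT-O analysis is the MMRM, and the multiple testing procedure in SAP 4.2.1 covers only PFS, PFS2 and OS.
- Omitting baseline from an ANOVA in a randomised trial costs precision and does not cause bias.
- PRO collection stopped after the primary analysis (protocol 6.5), and SAP section 5 describes the PFS analysis as past. The AUC may already have been run, so a change now would be a correction to a planned analysis.
- Using 24 months for deaths and the last visit for survivors looks dependent on outcome. It does, however, follow one principle: divide by the span over which the area was taken. The straight line from last visit to death remains a choice that should be stated.

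**Conclusion.** The concern holds. Read literally, the rule gives a dead patient a TOI of 48 and divides by a period that ends before death, so death raises the time-adjusted AUC and can push it beyond the scale: 167 instead of 27 in the first example, 452 instead of 11.5 in the second. That death cannot lower the result needs no assumption about the imputed score beyond its being non-negative. The figure of 48 rests on reading the zeros as raw responses and on placing five items in the ovarian subscale by elimination. The individual results rest on the assumed TOI and timings. The direction of bias, towards the arm with more deaths, is clear; its size in this trial cannot be determined from the documents.

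This should be corrected because the analysis reports its own p-value, but no primary or multiplicity-controlled result depends on it. The missing baseline covariate is a secondary matter of precision.

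**What to change.** Change three sentences in SAP 4.2.9:

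1. Set the scored TOI, after reversal, to 0 from death to 24 months, in place of zeroing the questions. State whether the first zero falls at the date of death or at the next scheduled visit.
2. For patients who die within 24 months, divide the AUC by 24 months. Keep the last-visit divisor for survivors.
3. Fit an ANCOVA with baseline TOI and the stratification factor.

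The cost is SAP text and minor code; no new data are needed. If the analysis has already been run, check how the program handled both the zeros and the divisor. If it was coded as written, rerun it and report the change as a correction.

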4.2.10 Exploratory analyses

EO-5D-5L

The evaluable population will comprise all patients in the FAS (ITT population).

Descriptive statistics will be calculated for each scheduled visit/time point in the study, for each trial arm and as a total. These will report the number of patients, the number of EQ-5D questionnaires completed at each visit, the number and proportion responding to each dimension of the EQ-5D-5L. Additionally summary statistics (e.g. n, mean, median, StD, min, max) will be reported for the EQ-5D index score and the EQ-VAS score, and the change from baseline for the EQ-5D index score and the EQ-VAS score.

Graphical plots of the mean EQ-5D index score and EQ-VAS score, including change from baseline, and associated 95% CI by scheduled visits/time points in the study will be produced. To support submissions to payers, additional analyses may be undertaken and these will be outlined in a separate Payer Analysis Plan.

Health care resource use

The potential impact the disease and treatment has on health care resource use will be analysed for the purposes of submissions to payers. Descriptive statistics (as appropriate, including means, median, ranges or frequencies and percentages) will be provided for each arm on the different types of hospital admissions, the length of stay of people admitted in to hospital for at least one overnight stay and length of stay of people admitted to intensive care / high dependency units, as well as the primary sign or symptom the patient presents with. To support submissions to payers, additional analyses may be undertaken and these will be outlined in a separate Payer Analysis Plan.

Tumour BRCA

A summary table will be produced comparing BRCA mutation/s in tumour to germline BRCA mutation status.

Subsequent therapy

Subsequent therapies received after discontinuation of olaparib will be summarised and listed by treatment group, together with number of regimens received. Patients who subsequently received a PARP inhibitor or entered a PARP inhibitor trial will be summarised and listed by treatment arm according to line of subsequent therapy.

4.2.11 Safety

Safety data will be summarised and listed only. No formal statistical analyses will be performed on the safety data. All safety data will be summarised by actual treatment group (olaparib or placebo) including patients who have dose reduction for blinded period of study. Any patient who received an initial dose of olaparib will be included in the olaparib group, even if the patient was planned to receive placebo. Similarly, any patient who received an initial dose of placebo will be included in the placebo group, even if the patient was planned

to receive olaparib. However, some listings such as AEs listings will display the actual dose the patient received at onset of an AE.

Adverse events

All AEs, both in terms of Medical Dictionary for Regulatory Activities (MedDRA) preferred term and Common Toxicity Criteria for Adverse Events (CTCAE) grade, will be listed and summarised descriptively by count (n) and percentage (%) for each treatment arm. MedDRA dictionary will be used for coding. Any AE occurring before olaparib/placebo treatment (i.e. before Study Day 1) will be included in the AE listings, but will not be included in the summary tables (unless otherwise stated). These will be referred to as 'pre-treatment'.

The summary tables will include all AEs that occurred after the start of treatment up until the end of the 30 day follow-up period. The 30 day follow-up period will be defined as 30 days following discontinuation of olaparib/placebo treatment.

All reported AEs will be listed along with the date of onset, date of resolution (if AE is resolved), investigator's assessment of severity and relationship to study drug. Frequencies and percentages of patients reporting each preferred term will be presented (i.e. multiple events per patient will not be accounted for apart from on the episode level summaries).

Partially missing dates will be imputed as per the phUSE guidelines (http://www.phusewiki.org/wiki/index.php?title=Imputing Partial Dates)

For date of onset:

- Missing day Impute the 1st of the month unless month is same as month of first dose of study drug then impute first dose date
- Missing day and month impute 1st January unless year is the same as first dose date then impute first dose date
- Completely missing impute first dose date unless the end date suggests it could have started prior to this in which case impute the 1st January of the same year as the end date.

When imputing a start date ensures that the new imputed date is sensible i.e. is prior to the end date of the AE.

For date of resolution:

- Missing day Impute the last day of the month unless month is same as month of first dose of study drug then impute last dose date
- Missing day and month impute 31st December unless year is the same as first dose date then impute last dose date

Date 15 February 2022

• Completely Missing – need to look at whether the AE is still ongoing before imputing a date and also when it started in relation to study drug. If the ongoing flag is missing then assume that AE is still present (i.e. do not impute a date). If the AE has stopped and start date is prior to first dose date then impute the 1st dose date, if it started on or after first dose date then impute a date that is after the last dose date.

Summary information (the number and percent of patients by treatment) will be tabulated for:

- All AEs
- All AEs causally related to study medication
- AEs with CTCAE grade 3 or higher
- AEs with CTCAE grade 3 or higher, causally related to study medication
- AEs with outcome of death
- AEs with outcome of death causally related to study medication
- All serious adverse events (SAEs)
- All SAEs causally related to study medication
- AEs leading to discontinuation of olaparib/placebo
- AEs leading to discontinuation of olaparib/placebo, causally related to olaparib/placebo
- Other significant AEs
- Other significant AEs causally related to olaparib/placebo

An overall summary of the number and percentage of patients in each category will be presented, as will an overall summary of the number of episodes in each category. In addition, a truncated AE table of most common AEs, showing all events that occur in at least 5% of patients overall will be summarised by preferred term, by decreasing frequency. This cut-off may be modified after review of the data.

Each AE event rate (per 1000 patient years) will also be summarised by preferred term within each system organ class. For each preferred term, the event rate will be presented and will be defined as the number of patients with that AE divided by the sum of the duration from the start of treatment to 30 days after the last treatment dose (for patients without the event) and the time to the AE (for patients with the event) in each group multiplied by 1000.

Date 15 February 2022

AEs will be assigned CTCAE grades (National Cancer Institute (NCI) CTCAE version 4.0) and summaries of the number and percentage of patients will be provided by maximum reported CTCAE grade, system organ class, preferred term and actual treatment group. Fluctuations observed in CTCAE grades during study will be listed.

Summaries of the number and percentage of patients with AEs leading to dose modification of olaparib/placebo by preferred term and treatment group will be presented for the following:

- AEs leading to a dose reduction of olaparib/placebo
- AEs leading to a dose interruption of olaparib/placebo
- AEs leading to a dose modification, defined as a dose interruption and/or dose reduction of olaparib/placebo.

In addition, AEs with outcome of death, SAEs, AEs leading to discontinuation of treatment, AEs causally related to olaparib/placebo and OAEs will be listed.

A summary of deaths will be provided with number and percentage of patients by actual treatment group, categorised as:

- Death related to disease under investigation only
- Death related to disease under investigation only (death > 30 days after last treatment dose)
- AE with outcome of death only
- AE related to disease under investigation and with AE outcome of death
- AE with outcome of death only (AE start date falling >30 days after last treatment dose)
- Deaths > 30 days after last treatment dose, unrelated to AE or disease under investigation
- Deaths >30 days after last treatment dose, AE related to disease under investigation and with AE outcome of death,
- Patients with unknown reason for death.

A corresponding listing will also be produced.

A separate summary will be produced that presents any events that occur prior to dosing or starting more than 30 days after discontinuing therapy.

Summary tables will also be produced for the following common adverse events, based on grouped preferred terms:

- Anaemia
- Neutropenia
- Thrombocytopenia
- Nausea
- Vomiting
- Fatigue/Asthenia

The specific preferred terms to be included in the summaries will be provided prior to database lock.

Summary of long term tolerability

For each AE, median time to first onset of the AE will be presented in patients in the safety analysis set by actual treatment group. Patients who did not experience the AE will not be included in the summaries. Summary tables of time to first onset for each AE will also be produced (e.g. 1-28 days, 29-56 days, 57-84 days, 85-112 days, >112 days). Median duration of the AE will be presented in patients who experienced each AE.

Laboratory assessments

Box-plots of absolute values and change from baseline for a selection of continuous laboratory assessments will be presented.

For all continuous laboratory assessments, absolute value, change from baseline and percentage change from baseline will be summarised using descriptive statistics at each scheduled assessment time by actual treatment group. For categorical laboratory assessments, shift from baseline will be summarised using frequency and proportion at each scheduled assessment time by actual treatment group.

Shift tables for laboratory values by worst common toxicity criteria (CTC) grade will be produced, and for specific parameters separate shift tables indicating hyper- and hypodirectionality of change will be produced. For parameters with no CTCAE grading, shift tables from baseline to worst value on-treatment will be provided (i.e. on-treatment is defined as data collected up until 30 days after the last dose of olaparib/placebo).

A scatter plot of ALT versus total bilirubin, both expressed as multiples of ULN, will be produced. The scatter plot will be repeated for AST versus total bilirubin.

Liver biochemistry test results over time for patients with elevated ALT or AST, and elevated total bilirubin (at any time) will be plotted. Individual patient data where ALT or AST plus total bilirubin are elevated at any time will be listed also.

Urinalysis results (categorical data collected at baseline and only if clinically indicated post-baseline) will be listed only.

Clinically significant laboratory results will be flagged and listed. Reference ranges will also be listed. All laboratory summaries and listings will be presented by actual treatment group.

ECGs

ECG data will be listed by actual treatment group.

Vital signs

Vital signs (SBP, DBP, pulse rate, body temperature and weight) will be summarised over time in terms of absolute values and changes from baseline at each scheduled measurement by actual treatment group. Vital signs data will be listed by actual treatment group.

Selected safety data will also be summarised and listed at the time of each planned OS analysis.

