Age will be derived as age at last birthday in whole years using the date of randomisation and date of birth. Where a partial date of birth has been collected, the following imputation rules will be applied in order to calculate the patient's age for use in listings and summaries tables presenting age and/or age group and subgroup analyses based on age:

- If only the month and year of birth has been collected, the day of birth will be imputed as 15th
- If only the year of birth has been collected the day and month of birth will be imputed as 1st July
- If the date of birth is completely missing, the derived age of the patient will also be missing.

Date of birth will be listed as it has been collected on the eCRF.

Overall disease classification will be categorised as follows:

- If a patient has any site of metastic disease, they are classified as 'Metastatic',
- If a patient has no sites of metastatic disease and does have sites of local disease they are classified as 'local'
- Else if they have no sites of disease identified and no target lesions present at baseline and no non-target lesions present at baseline (as assessed by the investigator) and they do have a valid investigator assessed baseline scan, they are classified as 'NED',
- Else classified as 'unknown'

Partial dates for start and end of concomitant medications will be derived as per date of onset and date of resolution for adverse events, respectively.

Patients who were unblinded (a) prior to disease progression and (b) prior to or on the day of treatment discontinuation will be listed.

A listing containing both the eCRF BRCA results and the Myriad gBRCA and Foundation Medicine tBRCA results will be produced.

Patients disposition data will also be summarised and listed at the time of each planned OS analysis.

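### Partial adverse-event end dates in the month or year of first dose are imputed as the last dose date, which can fall outside the recorded month or year, or before onset

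*SAP*

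**What the plan says.** SAP 4.2.11 sets out rules for partial adverse-event dates, citing an external guideline as their source. For a resolution date with the day missing: "Impute the last day of the month unless month is same as month of first dose of study drug then impute last dose date". With day and month missing: "impute 31st December unless year is the same as first dose date then impute last dose date".

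The matching onset rule for a missing day is "Impute the 1st of the month unless month is same as month of first dose of study drug then impute first dose date".

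One plausibility check is stated: "When imputing a start date ensures that the new imputed date is sensible i.e. is prior to the end date of the AE". None is stated for end dates.

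Other parts of the SAP bear on the effect:

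- Summary tables count events from the start of treatment "up until the end of the 30 day follow-up period", so onset may follow the last dose.
- Under long-term tolerability in 4.2.11: "Median duration of the AE will be presented in patients who experienced each AE".
- At the end of 4.2.11: "Selected safety data will also be summarised and listed at the time of each planned OS analysis".
- In 4.2.12: "Partial dates for start and end of concomitant medications will be derived as per date of onset and date of resolution for adverse events, respectively".

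**The concern.** The onset rule tests against the first dose and inserts the first dose date, so the result stays in the recorded month or year. The two end-date rules make the same test but insert the last dose date, which need not lie in that period. Two errors follow.

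1. The event has a recorded end in the month (or year) of first dose, and treatment runs beyond it. The imputed end then overrides information the site supplied.
2. Treatment stops within that month or year, and the event begins after the last dose, during the 30-day follow-up. The imputed end then precedes onset.

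At stake are listed resolution dates, the median duration of each event and concomitant-medication end dates. The trigger picks out early events. Protocol 5.5.5 says that nausea and vomiting usually first appear in the first month and are intermittent, so short early events of this kind are exposed. In the first error the excess grows with time on treatment, so it would differ by arm if treatment length does.

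**Working it through.** The plan gives no figure to reproduce. The check applies the rules as written, reading month as calendar month with its year. All dates below are illustrative assumptions. Durations are inclusive: end minus onset plus 1.

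**Inputs from the documents.** The two end-date rules, the start-date check and the 30-day window come from SAP 4.2.11. Treatment for up to two years comes from SAP 1.2.

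**Error 1: end outside the recorded period.** First dose 10 March 2014, onset 12 March 2014, last dose 9 March 2016.

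| End as recorded | Imputed end | Imputed duration | Longest duration the record allows | Days past the recorded period |
|---|---|---|---|---|
| March 2014 | 9 March 2016 | 729 | 20 (12 to 31 March) | 709 |
| 2014 | 9 March 2016 | 729 | 295 (12 March to 31 December) | 434 |

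The last column is 729 − 20 = 709 and 729 − 295 = 434.

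**Error 2: end before onset.**

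- Day missing: first dose 3 March, last dose 5 March, onset 20 March, end recorded as March of that year. The imputed end is 5 March, 20 − 5 = 15 days before onset.
- Day and month missing: first dose 10 January 2014, last dose 5 March, onset 20 March, end recorded as 2014. The imputed end is again 5 March, 15 days before onset.

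In both cases onset is 15 days after the last dose, inside the 30-day window.

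**When the rule does no harm.** First dose 10 March 2014, onset 12 March, last dose 28 March, end recorded as March 2014. The imputed end is 28 March, a duration of 17 days, which the record allows.

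**How often the last dose leaves the recorded period.** First dose is taken as uniform over the days of 2014.

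| Days of treatment | Last dose outside first-dose month | Last dose outside first-dose year |
|---|---|---|
| 28 | 88.8% | 7.4% |
| 90 | 100% | 24.4% |
| 180 | 100% | 49.0% |
| 365 | 100% | 99.7% |
| 730 | 100% | 100% |

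So once treatment lasts more than about a month, error 1 is the normal result for any event that triggers the missing-day rule.

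**Effect on a median duration.** The documents do not give the share of records affected, so a share p is assumed. Take the least favourable case, in which every affected duration truly lies below the median and is moved above it. The reported median m′ then satisfies F(m′) = 0.5 + p, where F is the true distribution. If durations are exponential, reported over true median = −ln(0.5 − p) / ln 2.

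| p | True percentile reported as the median | Ratio to true median |
|---|---|---|
| 1% | 51st | 0.713 / 0.693 = 1.03 |
| 5% | 55th | 0.799 / 0.693 = 1.15 |
| 10% | 60th | 0.916 / 0.693 = 1.32 |

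**The case against.** The strongest reply is that few records can be involved and that the outputs are descriptive. Visits are weekly for the first four weeks, stop dates are collected for each event, and Protocol section 10 provides for queries on missing or impossible data. A resolved early event with its end day still missing should therefore be uncommon. Enrolment closed on 14 November 2014 apart from patients in screening, and the seven-year cut-off of March 2022 puts the last randomisation at about March 2015. Triggering end dates are therefore historic. Only selected safety data are repeated at the OS analyses, and the SAP does not say that durations are among them. The end-before-onset case needs very early discontinuation under the month rule. The cited guideline is not available here and may contain an end-date check.

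Most of this stands as a limit on size. Frequency is unknown, reuse is possible but not certain, and the median ratios are a worst case on assumed shares. It does not rescue the rule. The SAP writes the steps out, and a programmer who follows them gets the dates shown above. If the guideline says something else, the SAP should be corrected to match.

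It can also be said that a 31 December default may run past a patient's death. That is true, but the SAP already uses this default for every other year.

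**Conclusion.** The concern holds. As written, both end-date rules can give a date outside the recorded month or year, or before onset, and no stated check would catch either. The listed end date is wrong in every record of these two kinds. The effect on a median duration is small if partial dates are few: about 3% too long at a 1% share and 32% at 10%, on the worst-case exponential assumptions.

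Incidence, grade, time to onset and rates per 1000 patient-years do not use end dates, no formal safety test depends on them, and no efficacy result is touched. The text supports the conclusion with high confidence. The intended wording cannot be confirmed without the guideline. The correction should be made, but it does not threaten the trial's conclusions.

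**What to change.** In both end-date rules, remove the first-dose condition and impute the last day of the recorded month, or 31 December of the recorded year. If an exception using the last dose date is wanted, trigger it on the month or year of the last dose. Add a statement that an imputed end date may not fall outside the recorded month or year, nor before the onset or start date. Apply the same to concomitant medications in SAP 4.2.12.

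The cost is a short wording change and a small change to the date-imputation program. Durations and medication end dates may then differ slightly from those produced at the earlier data cut, and the report should say so.
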